4.5. Sample size

The primary outcome is the DRI. In order to detect a minimum clinically important difference of 8 points on the DRI (SD 20) [32, 39, 40] with 90% power and 5% statistical significance, 133 participants per group are required (calculated using nQuery). Accounting for 20% attrition at the primary endpoint of one year follow-up, the total recruitment target is 334 participants (167 per arm). Not all participants will be followed up at the 24 month time-point. Assuming two thirds of patients included in the primary analysis are followed up to two years, statistical power will be 75% for the group comparison at two years.

On 6th September 2021, the funder approved a request from the study team for a costed extension, with the proviso that the sample size be recalculated to provide 80% power. In order to detect a minimum clinically important difference of 8 points on the DRI (SD 20) with 80% power and 5% statistical significance, 100 participants per group are required. Accounting for 20% attrition at the primary endpoint of one year follow-up, the total recruitment target is 250 participants (125 per arm). An implication of the costed extension is that a higher proportion of patients will be followed up at the 24 month time-point. Assuming 80% of patients included in

the primary analysis model are followed up for the revised target, statistical power will be 71% for the group comparison at two years. Recruitment will continue beyond the target of 250 patients if that is met until the end of the recruitment period on 31st October 2023.

4.6. Participant recruitment

Figure 1 outlines the pilon fracture treatment flowchart and how it fits into our recruitment plans for the trial. Potentially eligible patients will be recruited from orthopaedic trauma clinics or wards, intensive care units and the emergency departments. The research team will work closely with the direct care team at each centre to optimise the screening (i.e. identification of potential participants) and recruitment for their local circumstances. A member of the patient's direct care team will first approach the patient about the study. Then the research nurse/associate will provide information about the study including an information sheet. An additional leaflet will also be available to patients who may want to know more about their pilon fracture, the treatment and possible recovery. Patients will have the opportunity to ask questions of the surgeon and the local research team. Consent will be sought for follow-up beyond the duration of the trial to allow the possibility of future long-term follow-up.

Person sustains closed pilon fracture Taken directly to trial MTC Arrives at District General A&E Assessment and CT for bony injury; or retain in plaster Referral to Trial centre from network hospital Multidisciplinary team Potentially eligible Surgeon identifies patients identified meeting, including research patient as eligible nurses. Discussion of by/to research nurse Patient eligibility for ACTIVE confirmed Patient Declines:

Patient approached about

Patient accepts. Enrolled via consultee /standard consent

ACTIVE

Figure 1: Pilon fracture treatment flowchart

Invited to give

reasons and/or qualitative interviews

4.6.1. Recruitment strategy

Our recruitment strategy will prioritise setting up MTCs during the recruitment phase of the trial. As part of our internal pilot phase we will pilot setting up Patient Identification Centres (PIC) for the Hull MTC site, which will involve setting up Hull's surrounding District General Hospitals, to refer eligible patients to Hull to enable them to be recruited into the trial. If this is found to be a feasible method of recruitment, we will set up PICs for other MTCs involved in ACTIVE. We will also provide MTCs with a letter to publicise the trial to referring hospitals. This is to manage treatment expectations of patients before their referral to the MTC and to encourage the continued referral of patients through the normal care pathway. Regional Trauma Networks will communicate to all Emergency Departments about the trial to encourage the referral of patients through the normal care pathway. A grid will also be available to sites that answers frequently asked questions that patients ask about the treatment options. We are also planning on setting up international sites to recruit patients into the trial.

Based on figures from a survey of interested MTCs, there are an estimated 384 cases per year (range 8 to 30 per centre). With 384 cases across 23 centres, this provides an average of 17 cases per centre per year, approximately 1.4 per centre per month. Based on data from other surgical trauma trials (Profher, HTA 06/404/53; FixDT, HTA 11/136/04) we have assumed that a conservative maximum of 50% will meet the trial inclusion criteria (192 cases). We have assumed a 70% recruitment rate as participants in both arms will receive a surgical intervention of similar intensity (DRAFFT, HTA 08/116/97; FixDT, HTA 11/136/04). This will provide an estimated maximum of 134 patients per year, on average 6 per site per year. Therefore if the assumptions hold our sample size of 334 should be achievable. The assumptions will be tested in the 12 month internal pilot.

4.6.2. Internal pilot

We will undertake a 12 month pilot study to test our assumptions about recruitment and confirm whether the trial is feasible. The internal pilot will be reviewed by the Data Monitoring Committee (DMEC) and the funder to determine whether the study progresses to the full trial. Recruitment data will be supplemented by a qualitative study on barriers and facilitators to recruitment and retention. The internal pilot and qualitative study will gather data to address the following questions: (i) are there a sufficient number of eligible patients identified and recruited in 12 months to make the trial viable within the proposed 36 month recruitment period; (ii) are there barriers to successful delivery and how can these be overcome.

At the end of the 12 month pilot we aim to have 15 sites set up and started recruiting, and a minimum of 65 patients recruited into the trial (on average 6 per centre per 12 month period).

We assume a staggered opening of recruitment sites over the 12 month pilot period (7 sites within the first 6 months and 8 further sites by month 12 of the pilot). Assuming 1.4 cases per site per month will result in 185 cases, if 50% of cases meet the trial inclusion criteria this provides an estimated pool of 93 eligible patients across 15 centres. We aim to recruit 70% giving a sample of 65.

If the assumptions are correct (93 eligible cases), we will be able to estimate a participation rate of 60 to 70% for the full trial to within a 95% confidence interval of $\pm 10\%$. This will inform discussions about the feasibility of the full trial.

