5.4.2. Internal pilot

The recruitment rate and 95% confidence interval (CI) will be estimated from the data collected. A CONSORT diagram will be constructed to show the flow of participants through the study

and the following outcomes calculated: number of eligible patients; proportion of eligible patients approached for consent; proportion of eligible patients not approached and reasons why; proportion of patients approached who provide consent; proportion of patients approached who do not provide consent; proportion of patients providing consent who are randomised; proportion of patients randomised who do not receive the randomly allocated treatment; proportion of patients dropping out between randomisation and follow-up. Data will be summarised on the reasons why eligible patients were not approached, reasons for patients declining to participate in the study; reasons why randomised patients did not receive their allocated treatment and reasons for drop-out, if available. Results will be compared against the study's recruitment assumptions and progression targets, and continuation of the trial or relevant modifications will be decided by the funding body.

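### The pilot target of 65 recruits is the upper end of the stated site-opening schedule, yet the protocol calls it a minimum

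*Protocol*

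**What the plan says.** Section 4.6.1 derives the case rate from 384 cases a year at 23 centres: "this provides an average of 17 cases per centre per year, approximately 1.4 per centre per month". It takes 50% of cases as eligible and 70% of those as recruited.

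Section 4.6.2 applies these rates to a 12-month pilot with 15 sites. On timing it says "We assume a staggered opening of recruitment sites over the 12 month pilot period", with "7 sites within the first 6 months and 8 further sites by month 12 of the pilot". The yield follows in three steps. The case count comes first: "Assuming 1.4 cases per site per month will result in 185 cases". The step to eligible patients is next: "if 50% of cases meet the trial inclusion criteria this provides an estimated pool of 93 eligible patients across 15 centres". The step to recruits is last: "We aim to recruit 70% giving a sample of 65". The aim for the end of the pilot is 15 open sites and "a minimum of 65 patients recruited into the trial", glossed as an average of 6 per centre per 12 months. The section adds that, given 93 eligible cases, a participation rate of 60 to 70% can be estimated to within ±10%.

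The pilot is reviewed by the data monitoring committee and the funder. Section 5.4.2 says "Results will be compared against the study's recruitment assumptions and progression targets", and the funding body then decides on continuation or modification.

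**The concern.** The number of cases depends on how many months the sites are open in total, and the protocol does not give that total. Working back from 185 cases gives the site-months of two fixed opening dates, each at the very start of its half-year. The sentence before it describes sites opening at some time within each window. Any spread inside those windows yields fewer patients.

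The label adds to the problem. Section 4.6.1 presents the 50% eligibility as a maximum and the yearly yield at 50% and 70% as an estimated maximum. Section 4.6.2 applies the same two rates to the most favourable site-months and calls the product a minimum.

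At stake is how the pilot is read. If sites open gradually and each recruits exactly as assumed, the headcount falls short of 65 although no assumption about eligibility or consent has failed. A headcount target cannot tell slow site opening from poor recruitment at open sites, and the two call for different remedies.

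**Working it through.** **Inputs (protocol, sections 4.6.1 and 4.6.2).** Case rate 1.4 per site per month; 50% eligible; 70% of eligible recruited; 7 sites in the first 6 months, 8 more by month 12; pilot length 12 months.

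**Formulas.** Cases = 1.4 × site-months. Eligible = 0.5 × cases. Recruits = 0.7 × eligible. Recruits per open site-month = 1.4 × 0.5 × 0.7 = 0.49, or 0.49 × 12 = 5.9 per site-year.

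**Reproducing the protocol.** 185 / 1.4 = 132.1 site-months. Seven sites open for 12 months and eight for 6 months give 7×12 + 8×6 = 132. Then 132 × 1.4 = 184.8 cases, × 0.5 = 92.4 eligible, × 0.7 = 64.7 recruits. This matches 185, 93 and 65 after rounding. All 15 sites open for the full 12 months would give 180 site-months, 252 cases and 88 recruits, so the protocol did not use that. The per-site figure also fits: 132 site-months are 11 site-years, and 65 / 11 = 5.9.

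**Other schedules that fit the text.** The protocol gives no dates, so each row below is an assumption.

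| Assumed opening | Site-months | Cases | Eligible | Recruits |
|---|---|---|---|---|
| All 7 at month 0, all 8 at month 6 (implied by 185) | 132 | 184.8 | 92.4 | 64.7 |
| Even within each half, one site at the start of each equal interval | 93 | 130.2 | 65.1 | 45.6 |
| All 15 even over 12 months (15×6) | 90 | 126.0 | 63.0 | 44.1 |
| Even within each half, on average mid-half (7×9 + 8×3) | 87 | 121.8 | 60.9 | 42.6 |
| Even within each half, one site at the end of each equal interval | 81 | 113.4 | 56.7 | 39.7 |
| Latest allowed: 7 at month 6, 8 at month 12 | 42 | 58.8 | 29.4 | 20.6 |

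The mid-half case is (132 − 87) / 132 = 34% below the protocol's figure.

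**Precision.** Half-width = 1.96 × √(p(1−p)/n).

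- n = 93: 0.0996 at p = 0.6 and 0.0931 at p = 0.7, so the stated ±10% is right for 93.
- n = 61: 0.1229 at p = 0.6 and 0.1150 at p = 0.7, or ±11.5 to ±12.3 points.

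**The case against.** The strongest reply is that nothing is miscalculated. The chain from 132 site-months to 65 recruits is exact, and seven sites followed by eight is itself a stagger. This stands as far as it goes: the fault is an undisclosed opening assumption that fits poorly with the sentence beside it, not a slip in multiplication.

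Second, the wording sets a latest date for the eight further sites and does not strictly bar them from opening before month 7. Section 8 also places six months of set-up before the pilot, so several sites could be ready on day 1. Both points are fair. They make 132 an upper end on the natural reading, not a mathematical bound. They do not make it a floor.

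Third, the harm is limited by what the protocol already plans. It states the rate of about 6 per centre per 12 months beside the headcount. Sections 4.8.1 and 5.4.2 collect and report numbers eligible, approached and consenting, with reasons. No automatic stop is tied to 65, and the ±10% is expressly conditional on 93 eligible cases. All of this stands and lowers the weight of the point.

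Fourth, the pilot is past. Section 8 puts it in months 7 to 18 from 1 September 2017, which ends about February 2019. Section 4.5 records a funder-approved extension on 6 September 2021. This also stands.

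**Conclusion.** The point holds in a limited form. The figures of 185, 93 and 65 require 132 site-months, which is the top of the stated schedule if the eight further sites belong to the second half-year. Calling 65 a minimum is therefore wrong on the natural reading. With even opening inside each half, the expected yield is about 43 recruits (roughly 40 to 46 across discrete even schedules), and the participation rate is known to about ±11.5 to ±12.3 points.

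A reader might infer more than this, and the documents do not support it:

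- That 43 is the correct target. It rests on an even spread that the protocol does not state. The latest openings allowed give about 21.
- That the per-site rate is wrong. It is consistent throughout; only the site-months are in question.
- That the trial's sample size or later accrual projections are affected. The targets of 334 and 250 come from power calculations, and the yearly projection of 134 in section 4.6.1 uses 23 centres for a full year.
- That the decision to continue was mistaken. The protocol reports no pilot results, and the trial went on to a costed extension.

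**What to change.** In section 4.6.2, do one of two things. Either state that 185, 93 and 65 assume seven sites open at month 0 and eight at month 6, and drop the word minimum; or give an explicit opening schedule and restate cases, eligible patients, recruits and precision for it.

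In either case, judge pilot recruitment against the protocol's own rate of 0.49 per open site-month (about 6 per site-year), and judge the number of sites opened separately against 15.

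The cost is one corrected paragraph and no new data. The stated yield looks less favourable if the second option is taken. As the pilot has ended by the protocol's dates, the change applies to the record and to how pilot performance is described in the trial report.

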4.7. Randomisation

Randomisation will be undertaken by York Trials Unit. When patients have consented and their baseline forms have been completed, the recruiting research associate/nurse/clinician will contact York Trials Unit (YTU), either by telephone or via the internet, to access a secure randomisation service. The randomisation service will record information and check patient eligibility to avoid inappropriate entry of patients into the trial. When a patient has a pilon fracture in both ankles, a specific ankle will be chosen prior to randomisation at the treating surgeon's discretion. YTU will then perform independent random allocation in a 1:1 ratio to internal fixation or external fixation, using computer generated random permuted blocks of random sizes, stratified by centre.

4.7.1. Allocation concealment and blinding

Patients and treating clinicians will be informed of the allocation. Web- or telephone-based randomisation will ensure concealment of the allocation sequence. However, as with many surgical trials, where the surgical site is clearly visible, it is not feasible to blind patients, surgeons or outcome assessors to their allocation. The primary outcome is a patient-reported measure. Outcome bias will also be mitigated somewhat by both groups of patients receiving routinely available surgical treatments. We will also collect data on patient and surgeon preferences; for patients we will also ask those who do not consent for their preferences for treatment. We will account for whether patients received their preferred treatment in a secondary analysis. Staff analysing questionnaire responses will be blind to patients' treatment allocation. All recruiting centres will have surgeons who are familiar with the two techniques and perform them as part of routine NHS care.

4.8. Data collection methods

Data will be collected at recruiting sites or by post from patients, then returned to YTU for scanning and processing. All reporting of data collection will be undertaken in line with the Consolidated Standards of Reporting Trials (CONSORT) statement. Data will be collected at baseline, 3, 6, 12 and 24 months post-randomisation.

4.8.1. Internal pilot data collection

Screening logs will be kept by participating centres throughout the trial. We will collect data on: number of eligible patients; proportion of eligible patients approached for consent; proportion of eligible patients not approached and reasons why; proportion of patients approached who provide consent; proportion of patients approached who do not provide consent and reasons why; proportion of patients providing consent who are randomised. We will also collect data on the proportion of patients randomised who do not receive the randomly allocated treatment and reasons why. Additionally, we will collect data on numbers of patients recruited with Cl, C2 and C3 subtypes. Experience in either surgical procedure will be collected from all surgeons, including the predominant procedure used for their patients. During site set up, the training delivered to sites will cover equipoise. The assumption of surgeon equipoise will be monitored during recruitment by scanning reasons for exclusion during screening and reasons for crossover following randomisation that may reflect surgeon preferences. This data will inform whether the study progresses from internal pilot to full study and will be used throughout the trial to monitor progress and identify potential areas to target to improve recruitment rates.

4.9. Follow up

Participants will be followed up at 3, 6 and 12 months post-randomisation. The primary follow-up point is 12 months post-randomisation. We will have an additional secondary outcome endpoint of 24 month follow up for all patients recruited except for those in the last year of the recruitment period. This will enable us to gather data for the secondary outcomes and economic analysis, whilst reducing costs and total length of the trial by 12 months. All follow-up will be undertaken through postal questionnaires. Follow-up data of patient questionnaires may also be collected at 3, 6, 12 and 24 months in NHS clinics where follow-up clinics form part of routine care, as necessary. Radiographs are those routinely used for the investigation of patients with a suspected fracture of the distal tibia and for the follow-up of such patients following any intervention, so there will be no need to request any additional or special investigations.

To minimise attrition, we will use multiple methods to keep in touch with patients. Firstly, if patients need help completing the questionnaires one of the study team can help them complete them over the telephone. This includes calling the patient if there is missing data on the primary outcome when the questionnaire is returned and other missing data as feasible. We will ask patients for full contact details (including mobile phone number and email address). A prenotification letter will be sent 2 weeks before the follow-up questionnaire is due at 3, 6, 12 and 24 months, to help prime participants and find out if they are no longer at that address. A text message reminder will also be sent on the day patients are expected to receive the postal questionnaire at 3, 6, 12 and 24 months. This has been shown to significantly reduce time to questionnaire response [41]. We will also send 2 and 4 week reminders. Where these methods fail we will give participants the option for completion of an abridged questionnaire (a minimum of the DRI and EQ-5D) via telephone or electronically after the 4 week reminder and will also contact them about this by SMS messaging. At 3, 6, and 24 month follow-up, we will include an unconditional incentive payment of £5 to maximize the completion and return of questionnaires. At 12 months this will increase to £20 to also cover expenses for attending the hospital clinic to perform imaging to assess bone healing [42]. We will also write newsletters during the trial to keep the participants informed and engaged with the trial which can enhance response rates [43].

A management system which will be used to track participant recruitment and study status as well as Case Report Form (CRF) returns. Data from CRFs will be processed by administrative personnel. Data will be verified through cross checking of the data against the hard copy of the CRF. The trial coordinator and statistician will write a Validation Plan for the CRFs in consultation with the YTU Data Manager. The Plan will include detailed coding for the CRFs and data query resolution rules/procedures. Quality Control will be applied at each stage of data handling to ensure that all data are reliable and have been processed correctly.

4.9.1. Short messaging service (SMS) sub-study to minimise attrition

We will undertake an embedded randomised controlled trial to evaluate the effectiveness of sending an SMS text message reminder with the option for participants to reply to, compared with a standard text message with no option to reply on postal questionnaire response rates. Participants will be randomised in a 1:1 ratio to receive either a text message with a reply option or the York Trials Unit standard text with no reply option with their 3-month follow-up questionnaires. The wording for the text with the reply option will read "ACTIVE Trial: you should have received a questionnaire in the post by now. Your answers are important; so please

help by returning it as soon as you can. To get in touch with us you can reply to this message. Thanks". The wording on the standard no-reply text will read "ACTIVE Trial: you should have received a questionnaire in the post by now. Your answers are important; so please help by returning it as soon as you can. Thanks". Participants will be sent the text messages at the same time as they are expected to receive their postal follow-up questionnaire (i.e., two to four days after the questionnaire is sent). Text messages are likely to be sent using secure UK-based text software such as that provided by Intelli message gateway (https://www.intellisoftware.co.uk). In the event that a message is not delivered, the sender will receive a notification, which will be used to classify the text message as "delivered" or "not delivered". The findings of this sub-study will be implemented during the course of this study. Once the results of this sub-study become available, participants will receive the text which demonstrated the highest questionnaire response rate, at subsequent follow-up time-points.

